## Appendix F EORTC QLQ-C30 and QLQ-MY20 items, scales and scores

### For QLQ-C30:

- Global health status:
  - Global health status/QOL (QL2):  $((Q29+Q30)/2-1)/6 * 100$
- Functional scales:
  - Physical functioning (PF2):  $(1 - (((Q1+Q2+Q3+Q4+Q5)/5) - 1)/3) * 100$
  - Role functioning (RF2):  $(1 - (((Q6+Q7)/2) - 1)/3) * 100$
  - Emotional functioning (EF):  $(1 - (((Q21+Q22+Q23+Q24)/4) - 1)/3) * 100$
  - Cognitive functioning (CF):  $(1 - (((Q20+Q25)/2) - 1)/3) * 100$
  - Social functioning (SF):  $(1 - (((Q26+Q27)/2) - 1)/3) * 100$
- Symptom scales/Items:
  - Fatigue (FA):  $((Q10+Q12+Q18)/3-1)/3 * 100$
  - Nausea and vomiting (NV):  $((Q14+Q15)/2-1)/3 * 100$
  - Pain (PA):  $((Q9+Q19)/2-1)/3 * 100$
  - Dyspnoea (DY):  $(Q8-1)/3 * 100$
  - Insomnia (SL):  $(Q11-1)/3 * 100$
  - Appetite loss (AP):  $(Q13-1)/3 * 100$
  - Constipation (CO):  $(Q16-1)/3 * 100$
  - Diarrhoea (DI):  $(Q17-1)/3 * 100$
  - Financial difficulties (FI):  $(Q28-1)/3 * 100$

## Scoring the EORTC QLQ-C30 version 3.0

**Table 1: Scoring the QLQ-C30 version 3.0**

	Scale	Number of items	Item range*	Version 3.0 Item numbers	Function scales
Global health status / QoL					
Global health status/QoL (revised)†	QL2	2	6	29, 30	
Functional scales					
Physical functioning (revised)†	PF2	5	3	1 to 5	F
Role functioning (revised)†	RF2	2	3	6, 7	F
Emotional functioning	EF	4	3	21 to 24	F
Cognitive functioning	CF	2	3	20, 25	F
Social functioning	SF	2	3	26, 27	F
Symptom scales / items					
Fatigue	FA	3	3	10, 12, 18	
Nausea and vomiting	NV	2	3	14, 15	
Pain	PA	2	3	9, 19	
Dyspnoea	DY	1	3	8	
Insomnia	SL	1	3	11	
Appetite loss	AP	1	3	13	
Constipation	CO	1	3	16	
Diarrhoea	DI	1	3	17	
Financial difficulties	FI	1	3	28	

\* **Item range** is the difference between the possible maximum and the minimum response to individual items; most items take values from 1 to 4, giving *range* = 3.

† (revised) scales are those that have been changed since version 1.0, and their short names are indicated in this manual by a suffix "2" – for example, PF2.

For all scales, the *Raw Score*, *RS*, is the mean of the component items:

$$Raw\ Score = RS = (I_1 + I_2 + \dots + I_n) / n$$

Then for **Functional scales**:

$$Score = \left[ 1 - \frac{(RS-1)}{range} \right] \times 100$$

and for **Symptom scales / items** and **Global health status / QoL**:

$$Score = \left\{ \frac{(RS-1)}{range} \right\} \times 100$$

### For QLQ-MY20:

- Functional scales:
  - Future perspective (MYFP):  $(1 - (((Q48+Q49+Q50)/3) - 1)/3) * 100$
  - Body image (MYBI):  $(1 - (Q47-1)/3) * 100$
- Symptom scales:
  - Disease symptoms (MYDS):  $(((Q31+Q32+Q33+Q34+Q35+Q36)/6)-1)/3 * 100$
  - Side effect of treatment (MYSE):  $(((Q37+Q38+Q39+Q40+Q41+Q42+Q43+Q44+Q45+Q46)/10)-1)/3 * 100$

**Scoring the QLQ-MY20 :**

Scale Subscale (abbreviation)	No. Items	Item Number(s)
Functional scales		
Future perspective (MYFP)	3	48 to 50
Body image (MYBI)	1	47
Symptom scales		
Disease symptoms (MYDS)	6	31 to 36
Side effects of treatment (MYSE)	10	37 to 46

**Handling of Missing items for QLQ-C30 and QLQ-MY20:**

- Multi-item Scales

Have at least half of the items from a given scale been answered?

- If Yes, use all the items that were completed, and apply the standard equations given above for calculating the scale scores; ignore any items with missing values when making the calculations.
- If No, set scale score to missing.

- Single-item Scales:

Set to missing if no response.

## Appendix G Definition of regions

### 1) Geographical regions

Western Europe	Eastern Europe	North America	Asia	Other countries
Belgium Denmark France Germany Greece Italy Norway Portugal Spain Sweden United Kingdom	Czech Republic Hungary Poland Slovakia	Canada United States	Japan Korea (Republic of) Taiwan (Province of China)	Australia New Zealand Turkey Russian Federation

### 2) Regulatory regions

Western countries	Other countries
Belgium Denmark France Germany Greece Italy Norway Portugal Spain Sweden United Kingdom Canada United States Australia New Zealand	Czech Republic Hungary Poland Slovakia Japan Korea (Republic of) Taiwan (Province of China) Russian Federation Turkey

## Appendix H Description of PFS2 analysis

**Table 19 - PFS2 analysis (progression based on investigator disease assessment)**

Situation	Date of progression or censoring	Outcome
No valid post-baseline disease assessments	Date of randomization	Censored
Death when further anti-myeloma treatment not yet started and prior to the cut-off date	Date of death	PFS2 event
No disease progression on study treatment* but disease progression or death after initiation of further anti-myeloma treatment and prior to the cut-off date	First progression date after initiation of further anti-myeloma therapy reported as per investigator or date of death if no progression after initiation of further anti-myeloma treatment	PFS2 event
No disease progression on study treatment*, no disease progression and no death after initiation of further anti-myeloma treatment and prior to the cut-off date	Earliest of the date of the last follow-up visit after initiation of further anti-myeloma treatment and the cut-off date. If no initiation of further anti-myeloma treatment, same date of censoring as for PFS on study treatment	Censored
Disease progression on study treatment*, no disease progression and no death after initiation of further anti-myeloma treatment and prior to the cut-off date	Earliest of the date of the last follow-up visit after initiation of further anti-myeloma treatment and the cut-off date. If no initiation of further anti-myeloma treatment, censor at the date of progression on study treatment	Censored
Disease progression on study treatment*, disease progression or death after initiation of further anti-myeloma treatment and prior to the cut-off date	First progression date after initiation of further anti-myeloma therapy reported as per investigator or date of death if no progression after initiation of further anti-myeloma treatment	PFS2 event

\* disease progression on study treatment or in follow-up but before initiation of further anti-myeloma treatment as per investigator including symptomatic deterioration

Signature Page for VV-CLIN-0528482 v3.0  
efc14335-16-1-9-sap

Approve & eSign

Approve & eSign

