6.2 DURATION OF STUDY PARTICIPATION

6.2.1 Duration of study participation for each patient

The patient will be considered in the study from informed consent signature until death consent withdrawal, or final OS cut-off date, whichever occurs first.

The duration of the study for a patient will include a period for screening of up to 21 days (or up to 28 days for FCBP). A cycle duration is 28 days. Patients will continue study treatment until disease progression, unacceptable AEs, patient wish, or any other reason. All adverse events occurring after informed consent signature will be reported up to 30 days after last study treatment administration.

After study treatment discontinuation, patients will return to the study site 30 days after the last dose of study treatments for end-of-treatment assessments, and 60 days after the last dose of study treatments for assessments including ADA (IPd arm only). If the ADA test at Day 60 is positive or inconclusive, ADA testing will be repeated every 30 days until negative (IPd arm only). If isatuximab is stopped prior to pomalidomide and dexamethasone, ADA will be tested on Day 1 of the 2 next cycles. If the ADA test at the second cycle administered without isatuximab is positive or inconclusive, ADA testing will be repeated every cycle until negative.

The related AEs and all SAEs regardless of relationship to study treatment ongoing at the time of study treatment discontinuation will be followed during the follow-up period until resolution or stabilization. During the follow-up period, any new related adverse events (regardless of seriousness) will be collected and followed until resolution or stabilization.

During FU, patients who discontinue study treatment due to progressive disease (PD) will be followed every 3 months (12 weeks) for further anti-myeloma therapy, second primary malignancies, and survival until death or final OS cut-off date, whichever comes first. Patients who discontinue the study treatment prior to documentation of PD will be followed-up monthly until confirmation of PD (even for patients who would initiate further anti-myeloma therapy without PD), and then every 3 months (12 weeks) for further anti-myeloma therapy, second primary malignancies, and survival, until death or final OS cut-off date, whichever comes first.

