#### *2.1.3.2.3 Other exploratory efficacy endpoints*

### **PFS2**

PFS2 is defined as time from the date of randomization to the date of first documentation of PD (as reported by the investigator) after initiation of further anti-myeloma treatment or death from any cause, whichever happens first. For patients alive without a progression after initiation of further anti-myeloma treatment before the analysis cut-off date, PFS2 will be censored at the date of the last follow-up visit not showing disease progression after initiation of further anti-myeloma treatment or the analysis cut-off date, whichever comes first. Additional details regarding the definition of PFS2 and handling of events and censoring are given in [Appendix H](#).

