#### **Time to Next Treatment**

TNT is defined as the time from randomization to the start of further anti-myeloma treatment. Patients who do not receive any further anti-myeloma treatment before the cut-off date will be censored at the date of their last FU visit or the cut-off date, whichever comes first. Patients with no FU visit will be censored at their last study treatment administration or the cut-off date whichever comes first.

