#### **2.4.4.3 Analyses of exploratory efficacy endpoints**

##### **PFS2 and PFS on first line of further therapy**

PFS2 and PFS on first line of further therapy will be analyzed at the time of second interim and final OS analyses. PFS2 will be analyzed using Kaplan-Meier methods, the hazard ratio and its 95% CI will be estimated using the Cox proportional hazards model stratified by stratification factors as entered in the IRT (ie, age and number of previous lines of therapy). P-value will be provided for descriptive purpose only. PFS on first line of further therapy will be summarized among patients who received at least one line of further therapy using Kaplan-Meier methods. It will be summarized separately for further therapy with daratumumab and non-daratumumab treatment.

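### SAP Table 19 censors progressed, untreated survivors back at first progression but counts deaths in the same state, so each arm's PFS2 curve is biased downward

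*SAP*

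**What the plan says.** SAP 2.1.3.2.3 starts PFS2 at randomization and ends it at investigator-reported progression "after initiation of further anti-myeloma treatment or death from any cause, whichever happens first". For patients without an event it says that "PFS2 will be censored at the date of the last follow-up visit not showing disease progression after initiation of further anti-myeloma treatment", or at the cut-off if earlier. That sentence gives no usable date for a patient who never started further treatment, and the section refers to Appendix H for detail.

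In Table 19 of Appendix H, one event row reads "Death when further anti-myeloma treatment not yet started and prior to the cut-off date". It is dated at death and makes no exception for patients who had already progressed. A later row covers patients who progressed and have had neither a further progression nor death after starting new therapy. Those who started it are censored at the last follow-up visit or the cut-off. For those who did not, the row says "If no initiation of further anti-myeloma treatment, censor at the date of progression on study treatment". The footnote defines the progression meant as "disease progression on study treatment or in follow-up but before initiation of further anti-myeloma treatment as per investigator including symptomatic deterioration".

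Two other places bear on this. Protocol 6.2.1 states that "patients who discontinue study treatment due to progressive disease (PD) will be followed every 3 months (12 weeks) for further anti-myeloma therapy", and also for survival. The SAP's time-to-next-treatment definition (2.1.9) states: "Patients who do not receive any further anti-myeloma treatment before the cut-off date will be censored at the date of their last FU visit", or at the cut-off if that is earlier. SAP 2.4.4.3 plans Kaplan-Meier estimates, a stratified hazard ratio and a confidence interval for PFS2 at the second interim and final OS analyses, and adds: "P-value will be provided for descriptive purpose only". No PFS2 sensitivity analysis is specified.

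**The concern.** Kaplan-Meier and Cox methods require that leaving the risk set at a given time does not depend on what happens to the patient afterwards. Under Table 19, whether a patient leaves at first progression is decided by later events. A patient who dies untreated stays at risk until death, and one who starts another line stays at risk through the wait. Only a patient who does neither is moved back. Between progression and next therapy, deaths stay in the numerator while survivors' time is taken out of the denominator.

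The deleted time is not doubtful. A PFS2 event needs either death or progression after further therapy has begun, so a patient seen alive and untreated has had no event by that contact. The usual reason for censoring back to the last disease assessment, that an event may have been missed, does not apply.

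At stake is the estimate of an endpoint that SAP version 3 added to evaluate the effect of study treatment on subsequent therapies. The interval affected is one that PFS2 is meant to include.

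**Working it through.** **1. The rows side by side.** All three patients have progressed and are untreated at that point.

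| Later course | Table 19 outcome | Time after progression |
|---|---|---|
| Dies before further therapy | Event at death | Kept |
| Starts further therapy | Event, or censored at last follow-up visit or cut-off | Kept, including the wait |
| Alive and untreated at cut-off | Censored at first progression | Deleted |

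**2. Hand example.** Ten patients progress at month 4 and none is treated. Five die at months 8, 12, 16, 20 and 24, and five are alive at month 30.

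- Censoring at last contact, with 10 at risk: S(8) = 9/10 = 0.90; S(12) = 0.90 × 8/9 = 0.80; then 0.70, 0.60 and S(24) = 0.50. The median is 24 months.
- Table 19 removes the five survivors at month 4, leaving 5 at risk: S(8) = 4/5 = 0.80; S(12) = 0.80 × 3/4 = 0.60; S(16) = 0.40; S(20) = 0.20; S(24) = 0. The median is 16 months.

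The five deaths are the same in both calculations.

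**3. Size at the planned cut-offs.** The documents give no PFS2 figure to reproduce. As a check on the design inputs, 4 × (1.960 + 1.282)² / (ln 0.6)² ≈ 161.1, which rounds up to the stated 162 PFS events.

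- From the documents: median PFS 4.0 and 6.67 months (SAP 1.3); 300 patients at 15 per month, so 300/15 = 20 months of accrual (Protocol 11.1); cut-offs at 43 and 51 months (SAP section 4).
- Assumed, because the documents are silent: 10% of first events are deaths; 10 to 40% of patients are never treated again; the mean gap to next therapy is 1 to 2 months; median survival while untreated after progression is 4 to 18 months; median time from next line to PFS2 event is 5 months.

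Results at 43 months, with 200,000 simulated patients per arm and scenario. The first three columns are the assumptions. In each arrow, the left value uses last-contact or cut-off censoring and the right value uses Table 19. S(36) is the proportion PFS2-free at 36 months.

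| Never treated | Mean gap (months) | Untreated median survival (months) | Arm | Progressed, alive, untreated | Median (months) | S(36) |
|---|---|---|---|---|---|---|
| 25% | 1.5 | 4 | Pd | 0.7% | 9.64 → 9.63 | 0.020 → 0.018 |
| | | | IPd | 1.6% | 12.77 → 12.75 | 0.064 → 0.059 |
| 10% | 1 | 9 | Pd | 1.4% | 10.77 → 10.71 | 0.032 → 0.023 |
| | | | IPd | 2.0% | 14.06 → 13.96 | 0.080 → 0.070 |
| 25% | 1.5 | 9 | Pd | 3.4% | 11.33 → 11.15 | 0.044 → 0.021 |
| | | | IPd | 4.6% | 14.62 → 14.38 | 0.095 → 0.068 |
| 25% | 1.5 | 18 | Pd | 8.2% | 12.60 → 11.95 | 0.091 → 0.025 |
| | | | IPd | 9.3% | 16.07 → 15.31 | 0.145 → 0.079 |
| 40% | 2 | 18 | Pd | 13.1% | 13.90 → 12.66 | 0.133 → 0.027 |
| | | | IPd | 14.8% | 17.70 → 16.26 | 0.188 → 0.080 |

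The median is low by 0.01 to 1.44 months and S(36) by 0.002 to 0.108. At 51 months the same scenarios give 0 to 1.08 months and 0.002 to 0.087. Censoring at last contact or cut-off reproduced the uncensored median at both cut-offs in every scenario.

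A separate simulation assumed 30% never treated, a mean wait of 3 months, mean untreated survival of 12 to 24 months and accrual over 17.6 months. At 43 months the control-arm median fell from 11.8 to 11.6 and from 13.7 to 13.0 months, and the experimental-arm median from 16.6 to 16.3 months. The loss is 0.2 to 0.7 months.

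**4. Hazard ratio.** This was simulated at 43 months with 20-month accrual and otherwise assumed inputs. The shift was 0.001 to 0.023 when mean untreated survival was 6 to 12 months. At 24 months it was 0.024 to 0.026 with 10% never treated, and about 0.06, toward IPd, with 30% never treated.

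**The case against.** The strongest reply is about weight. SAP 2.1.3.2.3 classes PFS2 as exploratory, although Table 10 lists it among other secondary endpoints. It lies outside the hierarchy of PFS, ORR and OS, and its p-value is descriptive. No confirmatory decision rests on it. That stands.

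The second reply is that the upper sizes rest on generous inputs. PFS2 cannot exceed OS, because every death is an event. In the 40% scenario the Pd median PFS2 is 13.9 months, above the design's 13.0-month control median OS (SAP 1.3). That corner therefore conflicts with the design assumption. It is not excluded, because the rationale for protocol amendment 06 expects survival to be longer than projected. The reply stands as a caution on the top of the range.

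Third, the reverse error is also tempting: calling the rule conservative because both curves fall. A lower curve in each arm says nothing certain about their ratio.

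None of these replies supplies a reason for the different treatment of deaths and survivors in Table 19.

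**Conclusion.** The rule makes censoring depend on the later outcome and lowers each arm's PFS2 curve. That follows from Table 19 and needs no assumption beyond some patients being progressed, untreated and alive at cut-off. The size does need assumptions: about 0 to 1.4 months on the median at 43 months, 0.2 to 0.7 in the second set of scenarios, near zero if next therapy is rapid, generally less at 51 months, and more in the tail than at the median.

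A reader might infer more than this, and the documents do not support it:

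- **That the PFS2 hazard ratio favors IPd.** The shift depends on how the alive, untreated share compares between arms, and the documents say nothing about that. The simulated shift of about 0.06 is one assumed corner.
- **That the trial's main conclusions are affected.** PFS, ORR, OS and the type I error do not use this rule.
- **That an error of more than a month should be expected.** Values near 1.4 months come from the extreme scenario above or from a 30-month cut-off, at which no PFS2 analysis is planned.
- **That all untreated patients are mishandled.** Those who have not progressed have their own row, which uses the PFS censoring date and is a separate matter.

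The point is a real and avoidable bias in an exploratory estimate.

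**What to change.** In Table 19, change only the clause for patients who progressed, are alive and have not started further therapy. Censor them at the date of the last follow-up visit or the cut-off date, whichever comes first. Add one sentence to SAP 2.1.3.2.3 giving the same date for untreated progressed patients, since the present text gives none. Leave the row for patients who have not progressed as it is. A condition about no second progression is not needed, because PFS2 recognizes progression only after further therapy begins.

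This matches the rule for time to next treatment and uses dates that the 12-weekly follow-up already collects. The cost is one table cell, one sentence and the matching line in the PFS2 derivation. If the sponsor prefers to keep Table 19 as the main PFS2 analysis, the revised rule should be added as a sensitivity analysis, with the number progressed, alive and untreated at cut-off reported by arm so that the size of the effect can be judged.
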